Between January 2011 and November 2013, 48 patients in the Dent Dizziness and Balance Center were diagnosed with Ménière's disease and were prescribed lamotrigine as an off-label treatment. These patients were given a definitive or probable diagnosis based on the AAO-HNS 1995 criteria and had experienced at least three attacks in the three months prior to treatment. Almost all patients had been previously seen by ENT or other specialists and had tried conventional treatments like an improved life style, a low-sodium diet and diuretics. Some patients even attempted surgical treatments. Dosages varied from 50-300mg daily; most patients experienced a reduction of vertigo attacks during titration, but if another attack occurred the dose was increased further. We found that 13 of the 48 patients (27.1%) were also diagnosed with some form of anxiety, six individuals (12.5%) with only migraine and 21 individuals (43.8%) with an anxiety disorder and migraine. Out of these 48 individuals, ten were lost to follow-up and four patients had side effects like rash and had to discontinue the medication. After removing the above 14 patients, 94.1% (32/34) of remaining individuals reported improvement in symptoms, especially a reduction of Ménière's vertigo attacks. Furthermore, 50% (16/32) of improved patients experienced complete vertigo attack remission. Before initiation of lamotrigine therapy, 48 patients reported a mean of 13.5 (SD=12.5) vertigo attacks in the preceding three months (Figure 1). Thirty-five of the patients completed the initial follow-up and

reported a mean of 4.9 (SD=7.2) vertigo attacks in the three months after starting lamotrigine, *p<0.0001 (Wilcoxon signed rank test). Twenty-eight patients reported a mean of 2.5 (SD=5.5) vertigo attacks after completion of a three-month maintenance dose, *p<0.0001 (compared to before lamotrigine). Vertigo attack reduction and remission was not affected by migraine comorbidity.

2.3 Provide the scientific or scholarly background for, rationale for, and significance of the research based on the existing literature and how will it add to existing knowledge.

Response:

Please refer to 2.1

2.4 Include complete specific citations/references.

Response:

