7.0 Study Timelines

7.1 Describe the duration of an individual subject's participation in the study.

Response:

The study is composed of five phases: medical history qualification (eight weeks), lead-in (four weeks), titration (six weeks), study period (12 weeks), and taper (two weeks).

7.2 Describe the duration anticipated to enroll all study subjects.

Response:

1-2 years

7.3 Describe the estimated date for the investigators to complete this study (complete primary analyses)

Response:

06/2016

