Participants who are diagnosed with Ménière's disease, as determined by clinical history, ENT confirmation and an audiogram, will qualify if they also have had two or more Ménière's vertigo attacks in a four-week span for two consecutive four-week periods (the qualification period). Those who meet these criteria will then need two or more Ménière's vertigo attacks during a four-week lead-in period to further establish a baseline and verify randomization eligibility. Participants are allowed from the beginning of the lead-in to take their choice of a symptomatic abortive medication according to its package instructions for Ménière's vertigo attacks that last longer than 30 minutes with nausea and/or vomiting. Symptomatic abortive medications include, but are not limited to, meclizine (Antivert), Valium, diazepam, or Zofran. The abortive medication can be used throughout the study regardless of treatment assignment and its use will be recorded. Twelve eligible participants, with a minimum total of six attacks during the qualification and lead-in periods, will be randomly assigned to either a placebo or lamotrigine treatment group. Randomization will be conducted by UBSoPPS Research Pharmacy. The study drug and matching placebo will be titrated from 25mg twice a day (BID) up to 150mg BID over a six week period. During titration, clinic visits are scheduled every two weeks to assess any adverse events, symptoms, quality of life, and compliance. Those who cannot tolerate the 150mg BID dose may return to a 100mg BID dose during an unplanned visit. However, if a participant is unable to tolerate the 100mg BID dose they will be withdrawn from the study. Participants will maintain the 150mg BID or 100mg BID dose for a 12-week period with clinic visits every four weeks to assess their progress. Between all study visits, participants are asked to complete a daily survey describing their symptoms. This survey is hosted by polleverywhere.com and can be completed through text message, an online website, or with a paper document- whatever method is preferred by the participant. At the conclusion of the 12-week study period, a study staff will be un-blinded

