11.0 Data Management

11.1 Describe the data analysis plan, including any statistical procedures.

Response: The primary response will be the number of vertigo attacks as measured at baseline and at the end of the study period. The secondary responses will include the percentage of vertigo free patients, audiograms, symptom severity scales and quality of life scales (listed in the Approach section). The analysis set will include all subjects who are randomized and receive at least one dose of the study medication or the placebo. Integer or continuous variables will be presented by their mean and median and their SD and IQR. Categorical variables will be summarized using counts and percentages. Demographic and baseline characteristics of the enrolled subjects will be summarized through descriptive statistics for continuous variables and through frequencies for categorical variables. Demographic and baseline characteristics of the intervention and placebo groups will be compared to assess for comparability. Continuous variables will be compared using Wilcoxon rank-sum test and categorical variables will be compared through Fisher's exact test. We will test for reduction in the Ménière's vertigo attacks from baseline through Wilcoxon's sign rank test and will compare the reduction between the two treatment groups using Wilcoxon rank-sum test. The tests will be two-tailed and the significance level will be set to 0.05. Additionally, we will perform statistical modeling of the number of vertigo attacks longitudinally through generalized linear mixed effects model using Poisson or Negative Binomial distribution as appropriate. Data analysis will be conducted using SAS (SAS Institute Inc., Cary, NC, USA) and R (http://www.r-project.org/). All data analyses will be performed by [name] of the SUNY UB Statistical Consultant Laboratory.

11.2 Provide a power analysis.

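### The primary response is a raw attack count with no stated window or exposure denominator, so early leaving reads as improvement

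*Combined protocol and SAP*

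**What the plan says.** Section 11.1 defines the outcome: "The primary response will be the number of vertigo attacks as measured at baseline and at the end of the study period". Section 8.1 adds only that the arms are compared on reduction from baseline; its >50% responder refers to frequency during treatment. Neither section gives a window for the attack count or divides it by time observed. The one measure scaled to 28 days is attack-free days, a secondary endpoint.

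The analysis population is clear: "The analysis set will include all subjects who are randomized and receive at least one dose of the study medication or the placebo". What a leaver contributes is not. Section 13.3 says nothing more is collected once a participant chooses to withdraw, and that partial withdrawal does not occur. The update in section 11.2 records two dropouts against eight completers and raises N to 16. Section 23.2 expects 2 to 5 dropouts.

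Several windows are available. Section 7.1 lists eight weeks of medical-history qualification, four of lead-in, six of titration and a 12-week study period. Section 9.1 requires attacks "during a four-week lead-in period to further establish a baseline and verify randomization eligibility", and pools the first 12 weeks only for eligibility, "with a minimum total of six attacks during the qualification and lead-in periods". Section 2.2 counts "vertigo attacks in the preceding three months" and in the three months after starting the drug; section 11.2 plans on the latter mean.

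The primary comparison is a rank-sum test on the reduction. The count model is an addition: "Additionally, we will perform statistical modeling of the number of vertigo attacks longitudinally". No offset is named, although section 9.1 says "During titration, clinic visits are scheduled every two weeks" and then moves to four-week intervals.

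**The concern.** A count that stops when the participant leaves is smaller because less time was observed. If it is subtracted from a full baseline count, the missing weeks appear as benefit. The plan requires a value for each dosed leaver and gives no other way to form one.

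At 8 per arm, one misclassified participant moves a responder rate by 12.5 points. The estimate, the responder comparison and some power are at stake. The window also matters for description: the same patient can show a large reduction or a large increase depending on which periods are paired.

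**Working it through.** **The plan's own figure.** Section 11.2 gives 86.6% power for N=12, means 5 v 13, SD 4. Negative binomial counts, 6 per arm, equal SD, log-link regression: 86.3% by likelihood ratio (89.1% by Wald). It reproduces. The calculation has no baseline, window or leaver, so it does not settle the present question and is not changed by it.

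**Windows, full follow-up.** Take 13 attacks per 12 weeks, unchanged or falling to 5 (means from section 11.2). Percent change = (end count / baseline count) − 1.

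| Baseline v end, weeks | Unchanged patient | Patient falling to 5 |
|---|---|---|
| 12 v 12 | 13 to 13: 0% | 13 to 5: −62% |
| 4 v 12 | 4.33 to 13: +200% | 4.33 to 5: +15% |
| 12 v last 4 | 13 to 4.33: −67% | 13 to 1.67: −87% |
| 12 v 18 (titration included) | 13 to 19.5: +50% | 13 to 7.5: −42% |

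As a rate, every row reads 0% and −62%.

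**Leavers, matched 12-week totals.** An unchanged patient leaving at week t of the study period shows a reduction of 1 − t/12: 83% at week 2, 67% at week 4, 33% at week 8. It exceeds 50% whenever t < 6. One such patient in an arm of 8 is 1/8 = 12.5 points.

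**False mean difference.** Suppose two of 8 leave in one arm only, at exit weeks uniform over 1 to 11 (mean 6), with no drug effect. Expected difference = (2/8) × (1 − 6/12) × mean untreated count. With 13 attacks: 0.25 × 0.5 × 13 = 1.6. With 21.6 attacks (see below): 2.7.

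**Simulation.** Inputs:
- 8 per arm; gamma patient rates with mean 13.5 per 12 weeks and shape 13.5²/(12.5² − 13.5) = 1.28 (section 2.2).
- Entry requires at least 2 attacks in each of three 4-week windows (section 9.1).
- Rate ratio 5/13; rank-sum test on absolute reduction.
- Assumed, not in the documents: within-patient 4-week gamma noise of shape 4; exits in weeks 1 to 11; leaving independent of attack rate; number of leavers per arm.

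| Matched 12-week windows | Raw count | Rate |
|---|---|---|
| Power, 1 v 1 leavers | 54% | 61% |
| Power, 2 v 2 leavers | 46% | 57% |
| False responder gap, 2 v 0, no effect | 11 points | 2 points |
| False mean difference, 2 v 0, no effect | 2.9 attacks | 0.1 attacks |

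The entry rule lifts these simulated patients to 23.2 attacks at baseline and 21.6 in untreated follow-up, above the 13 or so expected on placebo. Rescaled to about 13, power is 52% v 57% at 1 v 1 and 42% v 53% at 2 v 2, and the raw responder gap is again 11 points. Varying the noise (none, or shape 2) and the exits (weeks 1 to 8) gives losses of 5 to 8 points at 1 v 1 and 8 to 20 at 2 v 2.

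Type I error on raw counts is 1.3–4.2% at 1 v 1, 2 v 2 or 3 v 2, and 5.0–7.3% when both of two leavers are in one arm. Rates give 3.7–5.7%.

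**Does a window mismatch harm the primary test?** With no leavers, a 4-week baseline against a 12-week total gives a between-arm difference of 13.3 attacks (13.5 matched), type I error 5.9% in 1,500 replicates, and power 79% (64% matched). It does not. A rate on the 28-day baseline, by contrast, has only about 38% power.

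**The case against.** The intended reading can largely be guessed. Sections 2.2 and 11.2 work in three-month counts, section 7.1 fixes a 12-week study period, and qualification plus lead-in also makes 12 weeks. The objective and the responder definition speak of frequency. A final-four-week count does not fit planning means of 5 and 13. The survey is daily, so a rate can be computed later, and the mixed model would use the intervals that leavers complete. This stands as a guide to intent, but the plan never states it. The mixed model is additional to the primary test, and the three-month count after starting lamotrigine in section 2.2 includes titration.

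A rate is also not free. It gives nothing for someone who leaves in titration, and short diaries are noisy. That stands and shapes the fix.

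A reader might go further and infer that the primary test is invalid, or that pairing a 4-week baseline with a 12-week total biases the treatment comparison. The documents support neither. With full follow-up, the mismatch falls on both arms alike and cancels in the between-arm difference. An apparent reduction produced by equal leaving also cancels between arms, and part of it is regression to the mean, which rates show too.

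**Conclusion.** The point holds as a defect of definition with real but bounded consequences. Raw counts, applied to the stated analysis set, turn early exit into reduction. The 12.5-point effect per early leaver is plain arithmetic on 12-week totals. At central noise the power loss is roughly 7 to 12 points with one or two leavers per arm, nearer 5 at 1 v 1 in the lower-frequency population. One-sided leaving of two participants gives a false responder gap of about 11 points and a false mean difference of about 1.6 to 2.9 attacks. Type I error is a minor matter.

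Apart from the window and exit-week arithmetic, these sizes rest on assumed numbers, arms and timing of leavers, an assumed noise level, and leaving unrelated to attack rate. The documents do not give the two known dropouts by arm. Nothing here shows that the trial's comparison has in fact been biased.

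**What to change.** 1. In sections 8.1 and 11.1, define the primary response and the >50% responder as attacks per 28 observed days: the 12 weeks of qualification plus lead-in against the 12-week study period, stating that titration is excluded. Run the 28-day lead-in baseline as a sensitivity analysis; used alone it costs about 20 points of power. Note that the eight qualification weeks come from medical history, not diary, so the power advantage assumes the history is as accurate.
2. Put log(observed days) as an offset in the planned mixed model.
3. State one rule for participants with little or no study-period diary, including those who leave in titration: no change from baseline, hence non-responder. Type I error stays at 4.0–5.4%. Against dropping such participants, power is 53% v 58% at 1 v 1, 38% v 49% at 2 v 2 and 27% v 56% at 2 v 0.
4. Have people blinded to outcome by arm fix these choices now, which excludes staff un-blinded at Visit 8, and report that this came after eight completions.
5. Optionally, continue the daily survey after the drug is stopped. Sections 9.1, 9.2 and 13.3 withdraw such participants from the study and would first have to be reconciled, with a consent amendment.
6. Separately, for secondary endpoints, section 9.2 gives questionnaires at Visits 3 to 7 only to participants judged compliant, while section 12.3 says every visit. Reconcile these so that continuing participants are assessed regardless of compliance.

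Items 1 to 4 are wording changes to the analysis plan and endpoints. What remains: short diaries give noisy rates, missed diary days are taken as uninformative, and rates do not correct dropout related to attack frequency.

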Drug therapies grounded in etiology theories of ischemia and hydrops include vasodilators and diuretics. Betahistine, a vasodilator, blocks H1 and H3 receptors and increases vestibular and cochlear blood flow to facilitate vestibular compensation and control vertigo (Strupp et al., 2008). Although Betahistine is able to control vertigo, it has not been shown to address any other MD symptoms (Kaylie, Jackson & Gardner, 2005). The drug has not been US FDA approved and side effects include stomach fullness and discomfort, diarrhea, nausea, and headaches (Sampson, 2003; Monzani, 2012; Quaranta et al., 1999). Alternatively, diuretics are prescribed to reabsorb the endolymph fluid causing endolymphatic hydrops. Long term, non-blind trials showed up to a 79% improvement in vertiginous symptoms with some improvement in hearing, but this may reflect the natural history of the disease (Thai-Van, Bounaix, & Fraysse, 2001). Other doubts about the benefits of diuretics arise from methodology flaws in many of the studies (Quaranta et al., 1999).

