3.0 Inclusion and Exclusion Criteria

3.1 Describe the criteria that define who will be included or excluded in your final study sample.

Respons Inclusion Criteria:

•Male and female participants aged 18 years or older

•Diagnosed with unilateral definite Ménière's disease according to the AAO-HNS 1995 criteria, confirmed by an ENT

•Active vertigo: at least two Ménière's vertigo attacks (defined as lasting 20 minutes or longer and associated with tinnitus, ear fullness, or low frequency hearing loss and nausea/vomiting) every four weeks during the eight-week qualification period and at least two or more Ménière's vertigo attacks during the lead-in phase prior to randomization

•Documented unilateral lower frequency hearing loss defined as the fourtone average (arithmetic mean rounded to the nearest whole number) of the pure-tone thresholds at 0.25, 0.5, 1 and 2 kHz more than or equal to 25 dB of the worse audiogram during the six months before screening

•Have tried diuretics for at least one month and discontinued treatment due to continued vertigo attacks

•All other co-existing medical or psychiatric conditions are stable, and no greater than moderate severity

•Willing to avoid pregnancy during the entirety of the study (abstinence or two forms of acceptable birth control, such as condoms and oral contraceptives)

Exclusion Criteria:

•Bilateral Ménière's disease

•Current or past history of migraine

•Any other neuro-otologic disease or major vestibular abnormality found during screening that could confound the evaluation of Ménière's symptoms

•Previous intolerance or sensitivity to lamotrigine

•On any prohibited medication within four weeks prior to the study

•History of tympanostomy tubes with evidence of perforation or lack of closure

•IT gentamicin injections or endolymphatic sac surgery within the last year

•History of or current immunodeficiency disease, nephrolithiasis, hypertension, cardiac disease, arrhythmia, hypercholesterolemia, hemiplegic/basilar migraine, stroke, diabetes, vascular disease or kidney disease

•Family history of unexplained deafness

•Pregnant or breastfeeding

•Current diseases or conditions that may be associated with an altered perception of processing stimuli

•Current severe medical condition(s) that in the view of the investigator prohibits participation

•Previously used the investigational drug

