•Current non-vertiginous dizziness (orthostatic or panic disorder) unless it could be clearly differentiated from Ménière's attacks by the participante:

3.2 Describe how individuals will be screened for eligibility.

Response:

[name] conducts and orders a physical exam and relevant testing to assure subjects meet criteria outlined.

Participants who are diagnosed with Ménière's disease, as determined by clinical history, ENT confirmation and an audiogram, will qualify if they also have had two or more Ménière's vertigo attacks in a four-week span for two consecutive four-week periods (the qualification period). Those who meet these criteria will then need two or more Ménière's vertigo attacks during a four-week lead-in period to further establish a baseline and verify randomization eligibility. Participants are allowed from the beginning of the lead-in to take their choice of a symptomatic abortive medication according to its package instructions for Ménière's vertigo attacks that last longer than 30 minutes with nausea and/or vomiting. Symptomatic abortive medications include, but are not limited to, meclizine (Antivert), Valium, diazepam, or Zofran.

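### The planned signed-rank test of reduction from baseline cannot be read as a lamotrigine effect, because the weeks that select participants also supply the baseline

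*Combined protocol and SAP*

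**What the plan says.** Section 11.1 lists two tests of the attack count in one sentence: it will test for a reduction in "vertigo attacks from baseline through Wilcoxon's sign rank test and will compare the reduction between the two treatment groups" by a rank-sum test. The first test is within participants, the second between arms. One sentence governs both: "The tests will be two-tailed and the significance level will be set to 0.05". The first test is not labelled descriptive, and 11.1 does not say whether it is run in each arm or on both arms together.

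Entry depends on the same outcome. Section 3.1 asks for at least two attacks "every four weeks during the eight-week qualification period and at least two or more Ménière's vertigo attacks during the lead-in phase", and Section 9.1 restates this as randomisation of participants "with a minimum total of six attacks during the qualification and lead-in periods". Section 3.2 gives the lead-in a double purpose: participants need "two or more Ménière's vertigo attacks during a four-week lead-in period to further establish a baseline and verify randomization eligibility".

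Section 11.1 measures the primary response at baseline and at the end of the study period, but gives no counting window for either. Section 7.1 gives eight weeks of qualification, four of lead-in, six of titration and a 12-week study period. The objective (1.1) and the primary endpoint (8.1) are comparisons of lamotrigine with placebo. Section 9.1 randomises 12 participants; the update in 11.2 asks for 16.

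**The concern.** Participants are admitted because their counts were high enough in certain weeks, and those weeks are then the reference against which later counts are judged. Nothing requires two attacks per block after randomisation. A count that had to clear a floor is on average higher than the same person's unrestricted count, so the mean falls even if every participant's underlying attack rate is unchanged. The hypothesis of no change is then false for reasons unrelated to treatment, in the placebo arm as much as in the lamotrigine arm.

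What is at stake is attribution. The fall in counts is real, so a small signed-rank p-value would be correct as a statement about change. It would be wrong as evidence about lamotrigine, and it says nothing on whether the reduction exceeds that on placebo. The same caution applies to the proportion with more than 50% reduction if it is read within one arm.

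**Working it through.** **The plan's own figure.** The plan states no error rate for the signed-rank test. The figure that can be checked is the power of the between-arm comparison in 11.2: N=12, means 5 and 13, SD 7.24, two-sided 0.05, stated as 57.6%. Simulating negative binomial regression with log link, equal arms, a common SD and a Wald test gives 57.4%. The table reproduces.

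**Direction, by arithmetic.** Suppose a person has a constant Poisson rate λ per four-week block. The expected count in a block that had to reach two is

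E[X | X ≥ 2] = λ(1 − e^−λ) / (1 − e^−λ − λe^−λ).

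- λ = 13.5/3 = 4.5 (the preliminary series mean in 2.2, per block): 4.5 × 0.98889 / 0.93890 = 4.74. The later expected count is 4.5, a fall of 1 − 4.5/4.74 = 5%.
- λ = 2 (a person whose rate equals the floor, assumed): 2 × 0.86466 / 0.59399 = 2.91. The fall is 1 − 2/2.91 = 31%.

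The fall is small for people well above the floor and large for those near it. Attacks that cluster in time add to it.

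**Attainable level.** Without ties, an exact two-sided signed-rank test at 0.05 has level 2 × 1/64 = 3.1% with six participants and 2 × 5/256 = 3.9% with eight. Small arms therefore start below 5%.

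**Size, by simulation with no drug effect.** Person rates are gamma distributed. Block counts are Poisson, or overdispersed, or share a period multiplier so that attacks cluster. Only people with at least two attacks in each of three blocks are kept. The baseline total is compared with a later total of equal length by the exact two-sided signed-rank test at 0.05, with 2,500 to 3,000 trials per setting. Columns 6 and 8 are one arm at N=12 and N=16; columns 12 and 16 apply if the test is pooled over arms. Entries are the percentage of tests that reject.

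| Setting | n=6 | n=8 | n=12 | n=16 |
|---|---|---|---|---|
| No entry rule (check) | 1.4–1.5 | 3.3–3.6 | 3.8–5.0 | 4.7–5.0 |
| 12-week baseline; 13.5 (SD 12.5) is the population before selection | 3.0–4.5 | 5.3–9.0 | 7.4–12.8 | 7.8–16.0 |
| 12-week baseline; recruits' own baseline mean is 13.5 | 4.3–15.9 | 8.8–30.2 | 14.0–44.8 | 18.4–57.9 |
| 12-week baseline; population mean 6 to 20 per 12 weeks | 2.1–18.4 | 4.6–34.4 | 5.6–54.1 | 6.2–67.2 |
| Lead-in-only baseline against a 4-week end window | 1.3–9.0 | 3.3–17.6 | 4.6–26.2 | 5.6–35.3 |

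With recruits' baseline at 13.5, the mean falls 9% to 10% if each person's rate is constant and Poisson, and 17% to 30% if attacks are overdispersed or cluster. Without the entry rule the test keeps its level, so the rule causes the excess.

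**Responders.** With assumed 12-week source mean/SD of 13.5/12.5, 8/7 and 6/5, and month-to-month within-person CV of 0, 0.5 and 0.8, 5% to 39% of untreated participants show more than 50% reduction.

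**The primary comparison.** With 6 v 6 participants selected by the same rule, the rank-sum test rejects in 2.9% to 4.3% of null trials. Selection acts equally on both arms and cancels.

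**The case against.** The best defence is that inference already rests on the right test. The objective and the primary endpoint are between-arm comparisons, the responder rate is listed in 8.1 under comparisons with placebo, and nothing in 11.1 says the signed-rank result supports efficacy. That stands, and it keeps this from being a flaw in the primary analysis. It does not give the signed-rank p-value a use: 11.1 sets it at the same significance level, with no rule on how the two results are to be read together.

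A second defence is that 11.1 never says the three blocks form the baseline. Daily recording starts only in the lead-in, so a lead-in-only baseline is a fair reading. That also stands, and it roughly halves the upper figures. It does not remove the mechanism, because the lead-in has its own floor of two attacks.

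Third, over-rejection is not unconditional. With six per arm and the preliminary series taken as the source population, rejection stays at 3.0% to 4.5%.

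A reader might also infer four stronger things that the documents do not support:

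- That the main result is biased. It is not; the rank-sum test keeps its level.
- That a significant within-arm result beside a non-significant between-arm result is the expected outcome. With no drug effect, that pattern arose in 2% to 13% of simulated trials at 6 per arm and 3% to 26% at 8 per arm.
- That the same selection produced the preliminary p<0.0001. That series used a different entry rule (three attacks in three months). Its means fell by (13.5 − 4.9)/13.5 = 64% and (13.5 − 2.5)/13.5 = 81%, with different numbers followed up, which is more than selection gave in these simulations.
- That the background rejects earlier uncontrolled results on the same ground. Section 2.1 says of the non-blind diuretic trials "but this may reflect the natural history of the disease". This is a hedge about natural history, not a statement about selection on baseline counts.

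**Conclusion.** The point holds for the before-after test only. Because the selecting weeks supply the baseline, a fall is expected without a drug effect, and a significant signed-rank result can neither be credited to lamotrigine nor answer the stated objective.

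The direction follows from the entry rule; the size does not follow from the documents. Two-sided rejection with no effect is roughly 2% to 18% at 6 per arm and 5% to 34% at 8 per arm with a 12-week baseline, and about 1% to 9% and 3% to 18% with a lead-in-only baseline. It is near nominal if individual rates are stable and the source population matches 13.5 (SD 12.5). The upper ends need a lower source rate or attacks that cluster or are overdispersed. These ranges rest on assumed within-person variability and an assumed counting window. The change should be made, but the primary analysis does not depend on it.

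**What to change.** In Section 11.1:

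1. Define the counting windows for the baseline and the end of the study period.
2. Replace the signed-rank test with a descriptive report of within-arm change (median, IQR and individual data) without a p-value.
3. State that efficacy conclusions, including those on the proportion with more than 50% reduction, rest only on the lamotrigine-placebo comparison.

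The cost is a few sentences. No data collection changes, the rank-sum test stays as it is, and the only loss is a p-value that does not address the objective. The windows should be fixed before counts are compared by arm.
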